4. PLANNED ANALYSES

The following analyses are planned:

- A. Part A: Analyses to determine the Maximum Tolerated Dose (MTD);
- B. Part B (I): Stage 1 (Interim Analysis) of the Simon's 2-stage design (Primary evaluation of Response Rate)

Interim analysis will be performed on the 12 patients of the first stage of part B. If seven or more responses will be observed in the first stage of part B, further 16 patients will be enrolled in the second stage of part B. If six or fewer responses will be observed during the first stage then the study will be stopped. Futility will be assessed in 12 patients after 3 cycles.

The Interim analysis will evaluate preliminary efficacy and safety and tolerability of Givinostat at the MTD after 3 cycles in 12 patients. Exploratory endpoints analysis will also be included with available data after 3 cycles.

- C. Part B (II): Stage 2 (Overall Analysis) of the Simon's 2-stage design (at the end of Part B).

Final analysis will be performed in all 28 patients enrolled in two stages of part B after 6 cycles.

No formal DB lock is planned neither for the 1st Cycle of Part A nor for Stage 1 (Simon's 2-Stage design) of Part B of the study.

Three different Output Templates will be presented for the 3 sets of analyses.

Document: PPD

Author: PPD

Version Number:

V2.2

Version Date:

21 March 2018

Template No: CS_TP_BS016 – Revision 3

Reference: CS_WI_BS005

Effective Date: 01May2012

Copyright © 2012 Quintiles Transnational Corp. All rights reserved.

The contents of this document are confidential and proprietary to Quintiles Transnational Corp. Unauthorized use, disclosure or reproduction is strictly prohibited.

5. ANALYSIS SETS

Agreement and authorization of patients included/excluded from each analysis set will be conducted prior to the database lock of the study during the Data Review Meeting.

The analysis sets are defined distinctly for each of the 3 planned analyses.

The number and percentage of the patients included in the analysis populations will be reported in a table showing the reason of exclusion for all patients enrolled into study. A listing of reasons of exclusion from analysis population will be provided.

Patients who sign an informed consent form but who do not start Study treatment for any reason, will be considered as “Screening Failures”. For these patients, a separate Table will be produced including the primary reason for screen failure and patient’s demographic information as per electronic CRF.

5.1. SAFETY ANALYSIS SET (SAF)

The Safety analysis set will include all enrolled patients who receive at least one dose of study medication. All safety analyses will be conducted on this population.

5.2. INTENT-TO-TREAT ANALYSIS SET (ITT)

The Intent-to-treat analysis set will include all recruited patients who receive at least one dose of study medication and from whom at least one post-baseline efficacy measurement is obtained.

Of note, patients who dropped the study due to drug-related TEAE(s) before that the post-baseline efficacy measurement is obtained (i.e. at C3D28 and/or at C6D28), will be considered in the ITT analysis set; in these cases, the post-baseline efficacy measurements (i.e. at C3D28 and/or at C6D28) will be considered as “No Response”, even if these assessments were not performed.

In addition, patients who have performed the visit when the post-baseline efficacy measurements (i.e. at C3D28 and/or at C6D28) had to be performed, but for which the following conditions will happen, will be excluded from the ITT analysis set:

- HCT > 45% or HCT ≤ 45% with phlebotomy(ies), AND
- at least 2 out of 4 assessments of the following will be not performed:
 - a) WBC count;

Document: PPD

Author: PPD

Version Number:

V2.2

Version Date:

21 March 2018

Template No: CS_TP_BS016 – Revision 3

Reference: CS_WI_BS005

Effective Date: 01May2012

Copyright © 2012 Quintiles Transnational Corp. All rights reserved.

The contents of this document are confidential and proprietary to Quintiles Transnational Corp. Unauthorized use, disclosure or reproduction is strictly prohibited.

- b) PLT count;
- c) Spleen evaluation by CT scan or MRI;
- d) Disease-related assessment by MPN-SAF.

This is due to the fact that is not possible to define a clinico-haematological response as per ELN response criteria in these cases.

All efficacy analyses will be conducted on this population and will be based on the *effective/actual* DL/daily doses of Givinostat at which each patient has been treated.

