3.5. DETERMINATION OF SAMPLE SIZE

A standard 3+3 design adopting a modified Fibonacci escalation schema is used in **Part A** [3, 4, 5].

Sample size for **Part B** is discussed for the primary endpoint defined as the Overall Response Rate after 3 cycles. Simon's 2-stage design is employed in **Part B** [6] with the aim of testing the "null hypothesis" that $RR \leq 0.50$ versus the "alternative" that $RR \geq 0.75$. Response rate was assessed as defined in paragraph 6.2.5.2 of the Study protocol version 3.0. Overall, up to 28 patients are to be recruited, 12 patients being enrolled in Stage 1. PV patients enrolled at the MTD in **Part A** can be counted towards Stage 1.

Under the "null hypothesis" (if $RR = 0.50$), the expected total sample size is 18.2 patients, the probability of early termination at the end of Stage-1 is 0.613 and the probability of rejecting the "null hypothesis" is 0.081 (the target for the type-I error being 0.100).

Under the "alternative hypothesis" (if $RR = 0.75$), the probability of rejecting the "null hypothesis" in favor of the "alternative" is 0.902 (the type-II error being 0.098).

After testing the treatment on 12 patients in Stage 1, if 6 or fewer patients responded to the treatment, the trial should be terminated rejecting the "alternative" that $RR \geq 0.75$. Otherwise, the trial should go on to Stage 2 enrolling a further 16 patients to a total of 28 patients.

If at the end of Stage-2, a total of 17 or fewer patients responded to the treatment, the "alternative hypothesis" that $RR \geq 0.75$ should be rejected; alternatively, if 18 or more patients responded, the "null hypothesis" that $RR \leq 0.50$ should be rejected.

Estimations were obtained from CRO proprietary software (based on SAS® 9.2) according to the

Document: PPD

Author: PPD

Version Number:

V2.2

Version Date:

21 March 2018

Template No: CS_TP_BS016 – Revision 3

Reference: CS_WI_BS005

Effective Date: 01May2012

Copyright © 2012 Quintiles Transnational Corp. All rights reserved.

The contents of this document are confidential and proprietary to Quintiles Transnational Corp. Unauthorized use, disclosure or reproduction is strictly prohibited.

algorithm proposed by R. Simon [6].

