Frequency and percentage of patients in each response category (CR, PR, no response (NR) for PV and ET; CR, major response, moderate response, minor response and NR rate for MF) will be presented at Cycle 3 Day 28 (C3D28). Of note, patients who dropped the study due to drug-related TEAE(s) before that the post-baseline efficacy measurement is obtained (i.e. at C3D28 and/or at C6D28), the post-baseline efficacy measurements (i.e. at C3D28 and/or at C6D28) will be considered as "No Response*", even if these assessments were not performed. "*" will allow to distinguish them from them from the therapeutic response evaluation result of "No Response", that will be reported without "*" (i.e. "No Response"). Other missing data will not be replaced, if not otherwise specified.

For **Part B** – Stage 1, Simon's design hypothesis will be evaluated by calculating the frequency and 95% CI of patients with a CR and/or PR at C3D28.

For Part B – Stage 2, the efficacy of Givinostat will be evaluated by means of a generalized linear model (logit link function and binomial distribution) adjusting for age, sex and disease type (PV, ET, MF). The therapeutic response will be collapsed in two categories in order to improve the model performance:

- For PV and ET:
 - a) "Responders" (i.e. CR and PR), and
 - b) "Not Responders" (i.e. NR);
- For MF:
 - a) "Responders" (i.e. CR, major response, moderate response and minor response), and
 - b) "Not Responders" (i.e. NR for MF).

In addition, the following primary safety parameters will be evaluated in **Part B after 3 cycles of treatment** (i.e. at the end of Cycles 3, or including data related to Cycles 1, 2 and 3) based on SAF analysis set:

- Number of patients experiencing AEs.
- Type, incidence, and severity of treatment-related AEs, graded according to CTCAE v. 4.03 (14th June 2010).

AEs will be coded using MedDRA dictionary (using the 20.1 version). AEs will be reported on a per patient basis. If a patient has more than one AE for a treatment that is coded to the same PT, the patient will be counted only once for that PT. Similarly, if a patient has more than one AE for a treatment within a SOC category, the patient will be counted only once in that SOC category. A patient with multiple CTCAE grades for an AE will be summarised under the maximum CTCAE grade recorded for the event.

Document: PPD

Author: PPD

Version Number:

V2.2

Version Date:

21 March 2018

Template No: CS_TP_BS016 – Revision 3

Reference: CS_WI_BS005

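### The set called ITT drops treated patients who cannot be documented responders, so the reported Part B response rate at Cycle 3 Day 28 is biased upward whenever such patients occur

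*SAP*

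**What the plan says.** Section 5.2 builds the ITT set in three steps.

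- **Entry.** The ITT population "will include all recruited patients who receive at least one dose of study medication and from whom at least one post-baseline efficacy measurement is obtained". The section identifies that measurement as the one at C3D28 and/or C6D28.
- **Put back as No Response.** Only "patients who dropped the study due to drug-related TEAE(s) before that the post-baseline efficacy measurement is obtained".
- **Taken out although the visit took place.** Patients whose haematocrit is above 45%, or at or below 45% with phlebotomy, and for whom "at least 2 out of 4 assessments of the following will be not performed": WBC, platelets, spleen imaging and MPN-SAF. The reason given is that an ELN response cannot be defined for them.

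The section then applies this set to all efficacy analyses. Section 17.2 repeats the drug-related TEAE rule and adds: "Other missing data will not be replaced, if not otherwise specified". Appendix 1 makes the size of the analysis set the default denominator for percentages. The per-protocol set (Section 5.3) is drawn from ITT patients.

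The design sections speak of fixed numbers. Section 3.5: "Overall, up to 28 patients are to be recruited, 12 patients being enrolled in Stage 1". Section 4: "Final analysis will be performed in all 28 patients enrolled in two stages of part B after 6 cycles". No section links the ITT set to the 12 and 28.

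**The concern.** Part B has one arm, and its response rate is read against a fixed 50%. Who is in the denominator therefore matters directly.

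A patient who stops before C3D28 because of progression, lack of benefit, an unrelated event or withdrawn consent has no documented response and disappears from the denominator. The second exclusion depends on the outcome itself: missing items remove a patient only if haematocrit has failed. With haematocrit below 45% without phlebotomy, the same gaps are harmless, because Section 16.3 grants a partial response on that criterion alone.

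Both rules shrink the denominator and leave the numerator untouched. The label ITT tells readers that this kind of selection has been avoided.

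**Working it through.** **1. The plan's design figures.** Inputs from Section 3.5: p0 = 0.50, p1 = 0.75, stop if 6 or fewer of 12 respond, reject the null if 18 or more of 28 respond.

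P(reject) = sum over x = 7 to 12 of Bin(x; 12, p) × P(Bin(16, p) ≥ 18 − x).

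- p = 0.50: early termination 0.613; expected size 12 + (1 − 0.6128) × 16 = 18.2; P(reject) = 0.0815.
- p = 0.75: P(reject) = 0.902.

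The SAP's 0.613, 18.2, 0.081 and 0.902 reproduce.

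**2. Whom the haematocrit rule removes.** Each of the four other items is met, failed or missing. With haematocrit failed, a partial response needs at least three of them met (Section 16.3).

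- Patterns with two or more missing: 6 × 4 + 4 × 2 + 1 = 33. At most two items can be observed as met, so none of the 33 shows a response.
- In 6 of the 33, exactly two are missing and both known items have failed. At most two could ever be met, so these patients are certain No Response. For them the stated reason for exclusion is false.
- Patterns with exactly one missing: 4 × 8 = 32. In 12 of these, two items are met and one has failed, so the status is undetermined, yet the patient is kept.

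The rule therefore does not follow its own rationale in either direction.

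**3. Effect on the reported rate.** With R documented responders among N treated and k excluded, the plan reports R/(N − k) instead of R/N. The SAP gives no exclusion rate, so k is an assumption.

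| Responders | k | Reported rate | Exact 95% CI |
|---|---|---|---|
| 17 | 0 | 17/28 = 60.7% | 40.6 to 78.5 |
| 17 | 2 | 17/26 = 65.4% | 44.3 to 82.8 |
| 17 | 3 | 17/25 = 68.0% | 46.5 to 85.1 |
| 17 | 5 | 17/23 = 73.9% | 51.6 to 89.8 |

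At k = 5 the interval excludes 50%, although 17 responders fail the Simon rule. At Stage 1, 6/12 = 50.0% becomes 6/11 = 54.5% or 6/10 = 60.0%.

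**4. Effect on the Simon decision.**

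- *Counts of 7 and 18 kept, 28 recruited, no replacement.* An excluded non-responder adds nothing to the count, exactly as if kept. At a true all-treated rate of 0.50 the type I error stays at 0.081.
- *Excluded patients replaced until 12 and 28 are evaluable (not stated in the SAP).* If a fraction d is excluded and all of them are non-responders, the evaluable rate is 0.50/(1 − d):

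| d (assumed) | Evaluable rate | P(reject) |
|---|---|---|
| 0.05 | 0.526 | 0.131 |
| 0.10 | 0.556 | 0.207 |
| 0.15 | 0.588 | 0.317 |

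**The case against.** **The decision rule is not loosened.** A reader might infer that the exclusions inflate the type I error. The documents do not support that. The rule is a count, Section 3.5 caps recruitment at 28, and the SAP provides for replacement only in Part A. Seventeen responders fail whether they are shown over 28 or over 25. This objection stands: the defect lies in the estimate, its interval and the Stage 2 model.

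**Excluded patients are not all non-responders.** Someone who fails haematocrit with two items met and two missing might truly be a partial responder. This also stands. What can be said is that no excluded patient has a documented response, so the reported rate is never below the documented rate among all treated.

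**The SAP softens the problem.** Section 16.10 records adverse event as the primary reason for stopping when several apply. Section 17.1 analyses events of unknown or missing relationship as related, which, if carried over to Section 5.2, would enlarge the group kept as No Response. A death from a drug-related TEAE is already covered. Section 5 requires a table and listing of exclusions, so the all-treated rate could be rebuilt. None of this covers unrelated events, progression or withdrawn consent, or changes the rate the plan will report.

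**Two further readings go too far.** The and/or between C3D28 and C6D28 might be taken to let an incomplete Cycle 6 visit cancel a valid Cycle 3 result. The text does not say so, and Section 5 defines the sets separately for each planned analysis, so the Stage 1 analysis is unaffected. It needs clarifying, no more. Likewise, that Part A patients at the MTD "can be counted towards Stage 1" is a design feature stated in Sections 3.1, 3.2 and 3.5. It is not a defect of the ITT set.

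**Conclusion.** The point holds for the estimate. As written, Section 5.2 removes treated patients in a way that can only raise the reported C3D28 response rate relative to the documented rate among all treated. The confidence interval and the Stage 2 logistic model inherit the shift. The per-protocol analysis cannot reveal it, because that set is a subset of the same patients.

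The size depends on how many such patients occur, which the SAP does not say. Three of 28 would move 60.7% to 68.0%; none would mean no bias. The argument takes response as the Section 16.3 criteria define it and leaves aside the Investigator override in that section.

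The type I error remains 0.081 under the count rule without replacement. The figures of 0.131 to 0.317 apply only under a replacement practice that the SAP does not describe. What the SAP does lack is a statement of how the ITT set relates to the 12 and 28.

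**What to change.** Change Sections 5.2 and 17.2 as follows:

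- For the primary C3D28 rate and the Simon rule, use all treated patients counted towards the 12 and 28.
- Count anyone without a documented complete or partial response at C3D28, for any reason, as a non-responder. A patient who fails haematocrit is a responder only if at least three of the other four items are documented as met.
- State that the limits of 7 of 12 and 18 of 28 apply to treated patients without replacement.
- State that C3D28 and C6D28 are judged separately.
- Keep the present definition as an evaluable set, for a sensitivity analysis.

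The cost is SAP wording and one extra table. The reported rate may be slightly lower, and patients whose true response is unknown will count against the drug. That is the conservative direction when the comparison is with a fixed 50%.

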17.2. PART B

The following primary efficacy parameters will be evaluated in **Part B after 3 cycles of treatment** (i.e. at the end of Cycle 3) based on ITT analysis set and PP analysis set:

- **For PV and ET (if any):** Complete response (CR) and partial response (PR) rate according to clinico-haematological ELN response criteria [1];
- **For MF (if any):** CR, major response, moderate response and minor response rate according to the EUMNET response criteria [7].

Note that only in case the enrolment in **Part A** is slow (i.e. < 5 patients enrolled in 3 months, the eligibility for this part of the study could be expanded to all patients with cMPN.

The clinico-haematological ELN response criteria [1] and EUMNET response criteria will be used to assess the preliminary efficacy of Givinostat (primary endpoint) after 3 cycles of treatment in **Part B** for PV/ET and MF patients, respectively.

In all cases, the medical judgment of the Investigator's is taken into account. In particular, if the Investigator's clinical response assessment – that takes into account the overall medical judgment of the

Document: PPD

Author: PPD

Version Number:

V2.2

Version Date:

21 March 2018

Template No: CS_TP_BS016 – Revision 3

Reference: CS_WI_BS005

Effective Date: 01May2012

Copyright © 2012 Quintiles Transnational Corp. All rights reserved.

The contents of this document are confidential and proprietary to Quintiles Transnational Corp. Unauthorized use, disclosure or reproduction is strictly prohibited.

specific patient's case - is not in agreement with the exact application of the clinico-haematological ELN or EUMNET response criteria, the Investigator's assessment will supersede the "mathematical" application of these criteria and used for analysis into study report. Also mathematical application of ELN response criteria (not agreed by the medical site team) will be analyzed.

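### SAP 5.2 defines one patient-level ITT set with a C3D28 and/or C6D28 exclusion trigger; read literally, conditions met only at C6D28 remove an evaluable C3D28 primary outcome from the final Part B analysis

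*SAP*

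**What the plan says.** Section 5.2 admits to the ITT set treated patients with at least one post-baseline efficacy measurement. It then takes out "patients who have performed the visit when the post-baseline efficacy measurements (i.e. at C3D28 and/or at C6D28) had to be performed" when two conditions hold together:

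- haematocrit is above 45%, or at most 45% with phlebotomy; and
- at least two of four assessments (WBC, platelets, spleen by CT or MRI, MPN-SAF) were not performed.

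The reason given is that an ELN response cannot be defined in such cases. The section closes by running every efficacy analysis on this population.

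Section 5 separates the analysis sets by the three planned analyses (Part A, Part B Stage 1, Part B Stage 2), not by visit. Section 17.2 places the Part B primary endpoint on this set ("i.e. at the end of Cycle 3) based on ITT analysis set and PP analysis set"), and section 18.2 uses the same set names for the C6D28 secondary endpoint. Section 5.3 makes PP a subset of ITT. Section 4 times the Stage 1 look after 3 cycles and the last analysis later: "Final analysis will be performed in all 28 patients enrolled in two stages of part B after 6 cycles". Section 3.5 declares success "if 18 or more patients responded" and gives no rule for fewer than 28 evaluable patients.

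**The concern.** The exclusion acts on the patient, not on a visit result. Suppose a patient has all five ELN items at C3D28, and at C6D28 attends with a haematocrit of 47%, no spleen scan and no questionnaire. Taken literally, that patient leaves the set on which the C3D28 primary endpoint is analysed, and leaves PP too. Membership for the primary endpoint would then depend on data collected 12 weeks later, and partly on an outcome, since failed or phlebotomy-assisted haematocrit is one of the conditions.

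The literal rule also treats patients unevenly. It reaches only those who attended the visit, so someone who leaves after C3D28 and never attends C6D28 keeps the C3D28 result. Final membership is agreed before database lock in an open-label study, when C3D28 responses are already known. At stake are the denominator of the primary response rate and, if the Simon count is taken on ITT, a decision that can turn on one patient.

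**Working it through.** **Does the text separate the visits?**

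| SAP place | Level at which it works |
|---|---|
| 5.2, exclusion rule | patient; trigger at either visit |
| 5.2, closing sentence | one population for all efficacy analyses |
| 5 | distinct sets per planned analysis |
| 17.2 (C3D28) and 18.2 (C6D28) | ITT and PP, no visit qualifier |
| 4 | Stage 1 after 3 cycles; final analysis after 6 cycles |

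The Part B Stage 2 analysis therefore covers both visits with one set. Stage 1 has its own set and is decided on C3D28 data, so a later event at C6D28 cannot alter it.

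**Inputs (section 3.5).** Stage 1: "After testing the treatment on 12 patients in Stage 1, if 6 or fewer patients responded to the treatment", the trial stops; otherwise it continues, "enrolling a further 16 patients to a total of 28 patients". Final bound 18 responders; null rate 0.50, alternative 0.75.

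**The plan's own figures.** Let b(n, x, p) be the binomial probability.

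- Early stopping at 0.50: sum of b(12, x, 0.50) for x = 0 to 6 = 0.6128 (plan: 0.613).
- Expected size at 0.50: 12 + (1 − 0.6128) × 16 = 18.20 (plan: 18.2).
- P(reject) = sum over x1 = 7 to 12 of b(12, x1, p) × P(X2 ≥ 18 − x1), with X2 binomial on 16. This gives 0.0815 at 0.50 (plan: 0.081) and 0.9017 at 0.75 (plan: 0.902).

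All reproduce.

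**Effect on the final count.** Leave the Stage 1 decision as taken, remove k of the 28 before the final count, and keep the bound at 18. The SAP gives no expected k; one or two is an assumption.

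The chance of passing Stage 1 and finishing on exactly 18 responders is 0.0407 at 0.50 and 0.0588 at 0.75.

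- One responder lost: power 0.9017 − 0.0588 = 0.8429; type I error 0.0815 − 0.0407 = 0.0407 after rounding.
- One patient lost at random: a rejection is lost only if the total is exactly 18 and the removed patient is a responder. Power 0.9017 − 0.0588 × 18/28 = 0.8639; type I error 0.0815 − 0.0407 × 18/28 = 0.0553.
- Two lost: same enumeration, with hypergeometric removal for the random case.

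| Patients lost (assumed) | Removal | Type I error at 0.50 | Power at 0.75 |
|---|---|---|---|
| 0 | none | 0.0815 | 0.9017 |
| 1 | random | 0.0553 | 0.8639 |
| 1 | responder | 0.0407 | 0.8429 |
| 2 | random | 0.0350 | 0.8040 |
| 2 | both responders | 0.0173 | 0.7415 |

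**Effect on the rate.** Losing one responder: 18/28 = 64.3% (exact 95% CI 44.1 to 81.4) becomes 17/27 = 63.0% (42.4 to 80.6), and the count drops below the bound. Losing one non-responder: 18/28 becomes 18/27 = 66.7%, or 17/28 = 60.7% becomes 17/27 = 63.0%; the count, and hence the Simon verdict, does not change.

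**The case against.** The strongest reply is that the rule was meant visit by visit. The same and/or wording appears in the preceding paragraph of 5.2, on drug-related dropouts, and in 17.2, 18.1 and 18.2. There it can sensibly refer only to the visit whose assessment is missing; otherwise an observed C3D28 response would be overwritten after a later dropout. The rationale, that no response can be defined, points the same way, and the patient in question does meet the inclusion rule of one post-baseline measurement. Appendix 1 also allows percentages among patients with a non-missing assessment if a table shell says so. All this makes a visit-by-visit intention plausible. It does not put it in the text: the dropout paragraph changes a result and keeps the patient, whereas the exclusion removes the patient from the set. Two programmers could build different primary populations.

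Several limits on the point stand in full:

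- A reader might infer that missing data at C6D28 are enough for removal. They are not. An attended visit, the haematocrit condition and at least two missing assessments are all required. WBC and platelets belong to the same local haematology panel as haematocrit (section 16.8), so the realistic route is spleen imaging and MPN-SAF both missing.
- That the count of 18 is taken on ITT is an inference from the sentence covering all efficacy analyses. Section 3.5 counts out of 28 patients, section 4 speaks of all 28 enrolled, and section 17.2 gives Stage 2 a generalized linear model without restating the bound. That model would lose the same patients.
- Exclusions are agreed before database lock, tabulated and listed with reasons, so any removal would be visible, though not prevented.

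**Conclusion.** The point holds as a defect in how 5.2 is fixed. Followed literally, it can delete an observed C3D28 primary outcome from the final Part B analysis and from PP, for a reason that does not apply to C3D28. The alternative reading is reasonable but unstated, so the primary population is not uniquely defined.

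The size is conditional. It depends on how many patients meet the conditions only at C6D28, which the SAP does not give, and on the bound of 18 being applied to ITT. With one or two such patients, power at 0.75 falls from 0.902 to 0.864 or 0.804 under random removal; 0.843 and 0.741 are the extreme in which every removed patient is a responder.

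Two stronger conclusions are tempting and not supported. One is that the Stage 1 decision could be undone: it is taken on C3D28 data with its own set. The other is that the rule could produce a false success: with the bound held at 18, removals can only lower the count, so type I error falls. What can be inflated is the reported response rate, when the removed patient is a C3D28 non-responder.

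**What to change.** Make the evaluability rule in 5.2 visit-specific. C3D28 membership is set from C3D28 data only, and a patient who meets the exclusion conditions only at C6D28 is left out of the C6D28 analysis alone. Replace the and/or trigger with a separate sentence for each visit, carry the same split into PP, and have 17.2 and 18.2 name the visit-specific set. State there also which set the bound of 18 is counted on, and what applies if fewer than 28 patients are evaluable.

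The cost is SAP wording and one population flag per visit. The downside is that the C3D28 and C6D28 denominators may differ, which a table footnote should explain.
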